Participants:

[figure not shown]
Inclusion Criteria: We will enroll 60 veterans with PTSD. To be eligible for the study, participants must meet current DSM-V diagnostic criteria for PTSD (American Psychiatric Association, 2013). PTSD will be established by interview using the Clinician Administered Posttraumatic Stress Disorder Scale for the DSM-V (CAPS-5; Weathers et al., 2013a). Participants must also indicate current difficulties with anger and aggression as indicated by a score of 20 or higher on the trait anger scale of the State Trait Anger Expression Inventory-2 (STAXI-2, Spielberger, 1999), indicating moderate to severe anger problems. Veterans from all eras will be eligible to participate.

Exclusion Criteria: Participants with a current diagnosis of bipolar disorder, psychotic disorder, or current substance use disorder with severe symptoms. Participants also must not have a seizure disorder and must not be taking any medications that would affect cognition or behavior on the aggression task, including pain medication, benzodiazepines, or antipsychotics. Participants also must not have a positive drug (e.g., amphetamine, opiates, and cocaine) or alcohol urine screen at the post-treatment session (see below), as these substances could affect performance on the study tasks implemented at that session. Finally, participants must not currently be receiving concurrent individual therapy or group therapy focused on anger and aggression and must not currently be participating in the modified TREC group offered at the West Haven VA (WHVA).

Research Design and Methods

For an overview of the time line for study procedures, see Figure 2.

Figure 2. Timeline of Study Procedures

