| Diagnostic Assessments | | | | | |
| Clinician Administered PTSD Scale for DSM-V: Past-Month Version (CAPS-5) | X | | | | |
| Structured Clinical Interview for DSM-5 Disorders-Research Version (SCID-5-RV) | X | | | | |
| Life Events Checklist-5 (LEC) | X | | | | |
| Primary Outcome Measures: Self-Report | | | | | |
| State Trait Anger Expression Inventory-2 (STAXI-2) | X | X | X | X | X |
| Buss-Perry Aggression Questionnaire (BPAQ) | X | X | X | X | X |
| Primary Outcome Measure: Experimental | | | | | |
| Taylor Reaction Time Task (TRT) | | | | X | |
| Secondary Outcome Measures | | | | | |
| Physiological Reactivity: Heart Rate, Skin Conductance | | | | X | |
| Emotion Regulation: State Difficulties in Emotion Regulation Scale (DERS-S) | | | | X | |
| Exploratory Outcome Measures | | | | | |
| Five Facet Mindfulness Questionnaire (FFMQ) | X | X | X | X | X |
| PTSD Checklist for the DSM-V (PCL-5) | X | X | X | X | X |
| Quantity-Frequency Variability Index (QFI) | X | X | X | X | X |
| Alcohol Dependency Scale (ADS) | X | X | X | X | X |

Baseline Session:

(a) PTSD, other psychiatric disorders, anger and aggression:

The DSM-V criteria for PTSD will be established using the Clinician Administered PTSD Scale: Past-Month Version (CAPS-5, Weathers et al., 2013a). The CAPS-5 will be used to confirm DSM-V PTSD diagnosis and to provide a continuous measure of PTSD severity (CAPS-5 total score). To facilitate the administration of the CAPS, participants will also complete the Life Events Checklist-5 (LEC; Weathers et al., 2013b), which is a self-report questionnaire used to assess the extent to which individuals experienced any of 17 different stressful or difficult life events (e.g., combat exposure, natural disaster, fire or explosion).

Participants will be assessed for psychiatric disorders at the baseline session using the Structured Clinical Interview for DSM-5 Disorders – Research Version (SCID-5-RV, First et al.,

2014). The information from the SCID will be used to exclude participants with severe psychiatric disorders (e.g., schizophrenia or bipolar disorder).

(b) Battery of Self-Report Questionnaires: Participants will also complete a battery of self-report questionnaires including assessments measuring anger and aggression, in addition to trait mindfulness, PTSD, and alcohol use:

- State Trait Anger Expression Inventory-2 (STAXI-2, Spielberger, 1999)
- Buss-Perry Aggression Questionnaire (BPAG; Buss and Perry, 1992)

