Primary Aim 1 Hypothesis 1.1: Participants assigned to MBSR will report decreased levels of self-reported anger and aggression at post-treatment and at the 3-month follow up compared to those assigned to the TREC group. Scores on the State Trait Anger Expression Inventory-2 and the Buss-Perry Aggression Questionnaire will be used as the primary outcome variables for self-report anger and aggression. Intent-to-treat analyses will be conducted for these outcomes, which will be examined separately. Bonferroni adjustments will be implemented to control for Type 1 error. These data will be analyzed using mixed effects models with treatment, time, and treatment x time interaction as fixed effects. Subject will be the clustering factor and it will be nested within therapy group which will also be considered random. Different variance-covariance structures will be considered and the best one selected based on Schwartz’ Bayesian Information Criterion (BIC). Mixed effects models are the preferred method for analyses of such data as they use all available data on an individual, give unbiased results under general missing data assumptions and provide flexibility in modeling the correlation structure within subject. Significant interactions will be examined further using post-hoc tests.

Primary Aim 1, Hypothesis 1.2: Participants assigned to MBSR will exhibit lower levels of anger and aggression on the TRT compared to those assigned to the TREC group. Mixed effects models will be used to compare the TREC group to the MBSR group on responses on the TRT: (1) mean shock level across the TRT, and (2) total number of “20” shocks chosen on the TRT following the same strategy as for primary aim 1 hypothesis 1.1.

Secondary Aim 1, Hypothesis 1.1: Those assigned to MBSR will exhibit significant decreases in HR and SCL and increases in emotion regulation compared to those assigned to the TREC group. Mixed effects models will be used to compare the TREC group to the MBSR group on physiological variables (HR, SCL) and emotion regulation (DERS-S) following the same strategy as for primary aim 1, hypothesis 1.1.

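### The plan does not state which primary outcomes its Bonferroni correction covers; for any choice, Holm's step-down procedure gives the same error control and never rejects fewer hypotheses

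*Combined protocol and SAP*

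**What the plan says.** Under Data Analyses, Primary Aim 1 Hypothesis 1.1, the plan takes the STAXI-2 and the BPAQ as its two primary self-report measures. It continues: "Intent-to-treat analyses will be conducted for these outcomes, which will be examined separately". The next sentence is the only one on multiplicity: "Bonferroni adjustments will be implemented to control for Type 1 error". The hypothesis claims a benefit "at post-treatment and at the 3-month follow up compared to those assigned to the TREC group". Each outcome is analysed in a mixed model with treatment, time and their interaction, and post-hoc tests follow a significant interaction.

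Hypothesis 1.2 compares the arms on two TRT variables, listed as "1) mean shock level across the TRT, and (2) total number of “20” shocks chosen on the TRT". It takes over the multiplicity rule only by cross-reference: "following the same strategy as for primary aim 1 hypothesis 1.1". Table 1 also classes the TRT as primary, under the row heading "Primary Outcome Measure: Experimental".

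The Participants section gives the sample size: "We will enroll 60 veterans with PTSD". Neither that section nor Sample Size and Power Considerations states a significance level, sidedness, effect size or power. The latter describes the trial as a pilot that may not establish significance and whose main purpose is to inform a larger trial.

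**The concern.** A Bonferroni rule is defined by its overall level and the number of tests it divides that level by. The plan gives neither, although four outcome variables sit under one primary aim. The false-positive risk for Primary Aim 1 therefore depends on a choice left to the analyst, possibly after the data are seen. A report that MBSR improved one of the primary outcomes could carry a 5% error rate or nearly twice that, and a reader could not tell which.

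The second issue does not depend on the first. Whatever the family, single-step Bonferroni gives up rejections that Holm would make at the same error rate. In a trial of 60 that loss is avoidable.

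**Working it through.** **Inputs.** From the plan: four primary outcome variables in two pairs, and 60 participants. Assumed, because the plan is silent: two-sided 5% as the overall level of each family; 30 per arm; normal test statistics; correlations of 0 to 0.9 within a pair and 0 to 0.7 between pairs; standardized effects of 0.5 to 0.8. The plan has no error rate or power figure of its own to reproduce.

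**Step 1. Error over Primary Aim 1 under each reading, no true effects.**

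- Separate pairs: each test at 0.05/2 = 0.025. Independent: 1 − (1 − 0.025)^4 = 9.6%. Upper bound: 4 × 0.025 = 10%.
- One family of four: each test at 0.05/4 = 0.0125. Independent: 1 − (1 − 0.0125)^4 = 4.9%. Upper bound: 4 × 0.0125 = 5%.

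Correlated statistics, simulated with 1,000,000 draws per row:

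| Correlation within / between pairs | Two pairs at 0.025 | Four at 0.0125 |
|---|---|---|
| 0.3 / 0.3 | 9.1% | 4.7% |
| 0.5 / 0.3 | 8.8% | 4.6% |
| 0.7 / 0.3 | 8.2% | 4.3% |
| 0.7 / 0.7 | 7.0% | 3.7% |
| 0.9 / 0.7 | 6.1% | 3.2% |

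Strong correlation is plausible within the TRT pair, because both variables come from the same 28 shock choices. A fair range for the separate-pairs reading is therefore about 6% to 10%.

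**Step 2. Why Holm dominates.** Order the k p-values from smallest to largest and compare them in turn with 0.05/k, 0.05/(k − 1), …, 0.05, stopping at the first failure.

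- Every threshold is at least 0.05/k, so any p-value that Bonferroni rejects, Holm also rejects.
- With m true null hypotheses, a false rejection requires the smallest of their p-values to be at most 0.05/m. That has probability at most m × 0.05/m = 5%, whatever the correlation.

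For a pair the thresholds are 0.025 and 0.05. For four they are 0.0125, 0.0167, 0.025 and 0.05.

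**Step 3. Size of the gain.** The expected statistic is d√(30/2). At d = 0.6 it is 2.324. At 0.0125 the critical value is 2.498, so power is Φ(2.324 − 2.498) = 43.1%. At 0.025 the critical value is 2.241, so power is Φ(2.324 − 2.241) = 53.3%. The Holm figures are simulated with correlation 0.4 between all outcomes, all four affected and clustering ignored. Per-outcome power:

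| Effect (SD) | Pairs, Bonferroni | Pairs, Holm | Four, Bonferroni | Four, Holm |
|---|---|---|---|---|
| 0.5 | 38.0% | 42.4% | 28.7% | 34.2% |
| 0.6 | 53.3% | 58.7% | 43.1% | 51.0% |
| 0.8 | 80.4% | 85.2% | 72.6% | 81.6% |

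**Step 4. Where Holm does not help.**

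- The chance of at least one rejection is the same for Holm and Bonferroni within a given family, because both start at the same threshold.
- If only one of the four outcomes is affected, at 0.6 SD, power for it is 43.1% with Bonferroni over four and 43.2% with Holm over four.
- Moving from pairs at 0.025 to Holm over four lowers the chance of at least one rejection at 0.6 SD from 85.5% to about 77%.
- Holm within each pair leaves the aim-wide error of Step 1 at 6% to 10%. The procedure does not settle the family.

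Therapy-group clustering lowers all the power figures. With groups of 6 and an assumed intra-class correlation of 0.05, the design effect is 1 + 5 × 0.05 = 1.25 and the effective size is 30/1.25 = 24 per arm. Power at 0.5 SD then falls from 38.0% to 30.5% at the 0.025 level, and from 28.7% to 22.2% at 0.0125.

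**The case against.** **The plan may already control the aim at 5%.** The cross-reference in Hypothesis 1.2 can be read as extending one correction over all four outcomes, and then nothing is inflated. This stands. A reader might infer that the plan definitely corrects within each hypothesis and so definitely carries an inflated error rate. In favour of that reading, the Bonferroni sentence directly follows one about the two self-report outcomes. Near-identical cross-reference wording is also used for the secondary heart rate, skin conductance and emotion regulation outcomes, which are unlikely to belong to the same family. But the text never says so, and the 6% to 10% is conditional on it.

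**Correcting per hypothesis is defensible.** Self-report and laboratory behaviour are separately stated hypotheses, and the plan sets no rule that success on any one of four outcomes counts as success. This also stands. The choice of family belongs to the sponsor; the defect is that it is not stated.

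**The two time points.** A reader might count post-treatment and 3-month comparisons as separate unadjusted tests and arrive at a larger error. The documents do not support that count: there is one model per outcome, and post-hoc tests come only after a significant interaction. Nor do they give a reason to make the 3-month contrast secondary, since Hypothesis 1.1 claims it explicitly.

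**Power.** A reader might infer that Holm over four beats whatever the plan now does. It beats Bonferroni over four. Against pairs at 0.025 it is stricter at the first step.

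**Pilot purpose.** The trial is meant mainly to yield effect sizes with confidence intervals, and intervals that match Holm are less simple. This lowers the stakes but does not remove the point, because the plan states directional primary hypotheses and promises Type 1 error control.

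**Conclusion.** The concern holds in two parts. First, the family and level of the Bonferroni correction are not stated. At an assumed two-sided 5%, the error over Primary Aim 1 is about 6% to 10% if each pair is corrected separately, and at most 5% if all four outcomes share one correction. Second, in either family plain Bonferroni is dominated by Holm. When all outcomes are affected by 0.5 to 0.8 SD, Holm adds roughly 4 to 6 percentage points of per-outcome power in families of two and 5 to 9 points in a family of four. The dominance is exact and needs no assumption about correlation. The power figures are illustrative: they assume 30 per arm, correlation 0.4 and no clustering. Because this is a pilot, the point is a worthwhile improvement to the analysis plan, not a threat to the trial.

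**What to change.** Replace Bonferroni with Holm's step-down procedure for the primary outcomes. State the overall significance level, its sidedness and the family the procedure covers. If one 5% error rate is intended for Primary Aim 1, apply Holm over the four outcomes. If each hypothesis is to have its own 5%, apply Holm within each pair and say that the aim as a whole is not controlled at 5%. For Holm to be applied, each outcome must contribute one defined test, so name the STAXI-2 score and the model term or contrast that supplies its p-value. The 3-month claim in Hypothesis 1.1 can stay as it is.

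The change is to analysis wording and needs no extra data. It has three costs. Simultaneous confidence intervals that match Holm are less simple than Bonferroni intervals, which matters somewhat because the trial intends to report intervals for effect sizes. The gain is close to nil if only one outcome responds. And if the intention was to test each pair at 0.025, choosing Holm over four gives up some chance of at least one positive finding (85.5% to about 77% at 0.6 SD) in return for 5% control over the aim.

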Trauma Scripting Procedure. After completing the diagnostic interviews (CAPS-5/SCID-5-RV), eligible participants will participate in a trauma-script development procedure as part of a well-validated, script-driven trauma imagery task (Pitman et al., 1987). For this procedure, participants will be asked to identify their most traumatic experience. If they identify more than one event, they will be asked to choose the one that they consider the most distressing. They will first be asked to describe the experience in writing using a script preparation form and then will be asked to indicate which of several different subjective visceral and muscular reactions (e.g., heart beating slower/faster, feeling sweaty, stomach in knots, feeling warm, hands trembling, tension in arms, nausea) may have accompanied the experience. Participants’ written responses will then be reviewed and they will be asked to clarify or expand on the details if necessary. After the session, a script lasting approximately 60 seconds in duration will be composed that portrays the traumatic experience in the second person, present tense, and incorporates the different visceral or muscular reactions. The script will then be audio recorded for playback

during the experimental portion of the post-treatment session. A research assistant (who will be named later upon being hired) will read the narrative scripts to be audio-recorded.

During this baseline session, participants will also complete a battery of self-report questionnaires (see below for full details) to assess baseline levels of anger and aggression.

Randomization Procedures. After participants have completed the Baseline Screening and Evaluation Session they will be randomized to either the TREC group or the MBSR group. To decrease the amount of time participants have to wait before starting group treatment, randomization will be implemented at the group level. That is, after 6 participants are recruited, they will be randomly assigned using urn randomization procedures, to either the TREC group or the MBSR group.

Post-treatment Session: After all participants have completed their assigned interventions (TREC or MBSR) they will be scheduled for the post-treatment session to be held in the biological studies laboratory at the WHVA. At this session, all participants will complete a battery of self-report questionnaires to assess post-treatment levels of anger and aggression (see below).

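### The H1.1 model names no therapy-group effect on change over time and no degrees-of-freedom method, so the treatment-by-time test may be anticonservative if groups differ in change

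*Combined protocol and SAP*

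**What the plan says.** Under Randomization Procedures, "randomization will be implemented at the group level": "after 6 participants are recruited, they will be randomly assigned using urn randomization procedures, to either the TREC group or the MBSR group". Under Inclusion Criteria, "We will enroll 60 veterans with PTSD".

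The Data Analyses section, Primary Aim 1 Hypothesis 1.1, analyses the STAXI-2 and BPAQ with "mixed effects models with treatment, time, and treatment x time interaction as fixed effects". The random part is: "Subject will be the clustering factor and it will be nested within therapy group which will also be considered random". It continues: "Different variance-covariance structures will be considered and the best one selected based on Schwartz’ Bayesian Information Criterion (BIC"). The next sentence justifies mixed models partly by their flexibility for correlation within subject. On follow-up testing it says: "Significant interactions will be examined further using post-hoc tests". A Bonferroni adjustment is promised, without an alpha level or the number of tests.

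Table 1 schedules both scales at five occasions: baseline, week 3, week 6, post-treatment and 3-month follow-up. The last paragraph of Sample Size and Power Considerations expects part of the variance in treatment effects to come from clustering within groups. It uses this only for sample size and gives no value of ρ.

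**The concern.** The treatment-by-time interaction compares the arms on change. A group effect that is the same at every visit is subtracted out of each change, so it adds nothing to the standard error of that test. Baseline is taken before participants are randomised and before the group meets. Any correlation produced by sharing a therapist and a group must therefore appear after baseline, that is, as variation between groups in change. This is the clustering of treatment effects that the sample size section foresees, and the written model has no named term for it.

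If only a group intercept is fitted, the gateway test has essentially the standard error of 60 individually randomised people. Chance differences between a handful of groups could then be read as a treatment effect. The estimate of ρ to be carried into the full-scale trial would also be the wrong one, because it would describe constant group differences and not clustering of change.

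**Working it through.** The plan states no type I error, alpha, power or ρ, so there is no figure of its own to reproduce.

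**Inputs from the documents.** 60 participants in groups of 6 give 60/6 = 10 groups; there are 5 visits.

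**Assumptions.** Five groups per arm (urn randomisation does not guarantee this), full groups, two-sided tests at 5%, or at 2.5% if Bonferroni covers two outcomes. Visit variance is scaled to 1, with subject variance 0.55. The group variance g is 0 at baseline and then persistent, and the residual variance is σ² = 0.45 − g. Values of g from 0 to 0.15 are illustrative.

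**Step 1: cancellation.** Take subject variance 0.5 and residual variance 0.5, with a constant group variance c.
- Post-minus-baseline interaction: SE = √(2 × 2 × 0.5/30) = 0.258. There is no c in the formula, and an exact generalised least squares calculation gave 0.2582 for c = 0, 0.05, 0.1, 0.2 and 0.5.
- Between-arm difference in level at post-treatment: SE = √(2 × 1/30 + 2c/5). This is 0.258 at c = 0 and 0.516 at c = 0.5, so the group intercept does count there.
- With about 20% dropout the interaction SE moves only from 0.27764 to 0.27767.

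**Step 2: type I error of the post-minus-baseline contrast under an intercept-only model.**
- True variance: V = 2(2σ²/30 + g/5).
- Model variance: M = 2(2s²/30), where s² is the expected residual mean square on (60 − 2) × (5 − 1) = 232 df. The pattern 0,1,1,1,1 centred over visits has sum of squares 0.8² + 4 × 0.2² = 0.80. Group deviations within arm have 8 df and each is shared by 6 people, so s² = σ² + 8 × 6 × 0.80g/232 = σ² + 0.166g.
- Type I error ≈ 2[1 − Φ(z/√(V/M))], with z = 1.960 or 2.241.

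| g | σ² | V | M | V/M | at 5% | at 2.5% |
|---|---|---|---|---|---|---|
| 0 | 0.45 | 0.0600 | 0.0600 | 1.00 | 5.0% | 2.5% |
| 0.05 | 0.40 | 0.0733 | 0.0544 | 1.35 | 9.1% | 5.3% |
| 0.10 | 0.35 | 0.0867 | 0.0489 | 1.77 | 14.1% | 9.2% |
| 0.15 | 0.30 | 0.1000 | 0.0433 | 2.31 | 19.7% | 14.0% |

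Simulation agrees: 4.7%, 9.5%, 14.0% and 19.8% at nominal 5%, and 5.5%, 9.2% and 14.2% at nominal 2.5% for the three non-zero values. The omnibus interaction over five visits rejected in 7.8%, 12.0% and 17.1% at nominal 5%.

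**Step 3: can a flexible within-subject covariance repair it?** Suppose the variance of change is estimated freely at subject level. The change-score correlation within group is ρ = g/(2σ² + g) = 0.059, 0.125 and 0.20. The design effect 1 + (6 − 1)ρ is 1.29, 1.63 and 2.00. Type I error is 2[1 − Φ(1.96/√DE)] = 8.5%, 12.4% and 16.6%; simulation gave 8.8%, 12.6% and 17.3%. It helps a little but does not supply the missing term.

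**Step 4: a group-level test.** A t-test on the ten group mean changes (8 df, critical value 2.306) rejected in about 5% of null trials in every scenario. The 8 df matter in themselves: using 1.96 with a t statistic on 8 df gives 8.6%.

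**The case against.** Several points on the other side are sound.

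- **The text does not say intercept only.** Therapy group is random, its form over time is unstated, and covariance structures are left to BIC. A reader might infer that the model contains only a constant group effect. That is the natural reading, and the remark on within-subject correlation suggests that the BIC search is at subject level, but the documents leave it open. This is under-specification and not a demonstrably wrong model.
- **Group randomisation is not ignored.** A reader might infer that the analysis fails to account for it. H1.1 is worded as a comparison at post-treatment and at follow-up, and such level comparisons do carry the group variance (Step 1). If the post-hoc test is the between-arm difference at the visit, which the plan does not define, a simulation requiring both a significant interaction and a post-treatment difference gave false positives in 1.2%, 2.6% and 4.0% of trials for g = 0.05, 0.10 and 0.15. Accepting a difference at either visit gave 2.2%, 3.9% and 5.6%. This stands, but only for that reading. A post-hoc contrast on change has no such protection, and a significant interaction is itself a reportable result.
- **Inflation is conditional.** It needs group-by-time variance above zero, and no ρ is given. At zero the test is nominal, however large the constant group effect.
- **Degrees of freedom depend on software.** None is named, so it cannot be said that the analysis would use a residual df of 232.
- **This is a pilot.** The sample size section says that significance may not be reached and that the purpose is planning. This lowers the severity. It does not remove the point, because H1.1 is a primary hypothesis with promised type I error control and the pilot is meant to inform later sample size work that needs ρ.

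**Conclusion.** The point holds as a conditional one and should be fixed. The plan does not specify a group-level random effect on change or a small-sample df method. If it is carried out as most naturally read, and if groups differ in change as the sample size section anticipates, the treatment-by-time test is anticonservative. For assumed group effects of 5% to 15% of visit variance, the post-minus-baseline contrast rejects in about 9% to 20% of null trials at nominal 5% (about 9% to 17% with the change variance freely estimated at subject level). At nominal 2.5% it rejects in about 5% to 14%, so Bonferroni does not cure it. These figures rest on ten full groups, five per arm, and a group effect that appears after baseline and persists.

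The documents do not support the flat statement that the trial's type I error is inflated, since neither the fitted group structure nor ρ is known.

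**What to change.** Amend the H1.1 paragraph of the Data Analyses section to:

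1. Specify a random therapy-group-by-time effect, or a group-level covariance for the post-baseline visits, plus subject within group. The post-baseline form, with baseline as a covariate, is safer. A single group-by-visit variance that is independent across visits understates a persistent effect: at g = 0.15 it averages to 0.2g (0.80g spread over 4 df), giving a contrast variance of 4(0.30/6 + 0.2 × 0.15)/5 = 0.064 against the true 0.100.
2. Keep the group terms in the model whatever BIC selects, and limit BIC to the within-subject structure.
3. Use Kenward-Roger degrees of freedom.
4. Name a fallback for non-convergence, which is likely enough with ten groups: compare baseline-adjusted therapy-group means with a t-test on the number of groups minus 2 (8 df with ten groups).
5. Define the post-hoc tests, and report the group-level variance of change with its uncertainty for the full-scale trial.

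The cost is SAP wording. The price in analysis is wider intervals and a critical value of about 2.31 in place of 1.96 at nominal 5%.

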- Five Facet Mindfulness Questionnaire (FFMQ; Baer et al., 2008)
- PTSD Checklist for the DSM-V (PCL-5; Weathers et al., 2013)
- Quantity-Frequency Variability Index (QFI; Cahalan, Cisin, & Crossley, 1969)
- Alcohol Dependency Scale (ADS; Skinner & Allen, 1982)

Interim Assessments: During the intervention period, at two time points (weeks 3 and 6 of therapy), participants will be asked to complete the STAXI-2, the BPAG, the FFMQ, the PCL-5, the QFI, and the ADS.

Post-treatment Session: Participants will complete the same battery of self-report questionnaires that was completed at the baseline session. In addition, participants also will complete the following assessments. (See Figure 3 below outlining the order of tasks during experimental portion of the post-treatment session.)

(c) Psychophysiological Assessments: During the experimental portion of the post-treatment session, physiological measurements will be recorded to assess reactivity during exposure to the trauma cue (script). Participants will sit quietly for 5 minutes to collect baseline (B) physiological assessments. This will be followed by the trauma-script reading (TR) and then the trauma-script imagery (TI) segments followed by a resting period (R) and assessment of subjective experiences.

Physiological measurements will include skin conductance levels (SC) and heart rate levels (HR). A BIOPAC MP150 system (BIOPAC, Santa Barbara, CA) that includes modules for HR and SC will be used to record physiologic analog signals. Physiologic analog signals will be digitized by an analog to digital converter. A notebook computer (IBM-compatible) with BIOPAC Acknowledge© software will be used to sample and store the digitized physiologic signals. Interbeat interval will be recorded in milliseconds via standard limb electrocardiogram leads connected to a High Gain Bioamplifier and converted to HR. Skin Conductance (SC) will be measured by an Isolated Skin Conductance coupler using a constant .5 V through 2, 9-mm (sensor diameter) Ag/AgCl electrodes filled with electroconductive gel placed on the hypothenar surface of the subject's non-dominant hand in accordance with published guidelines. The SC electrodes will be separated by 14 mm, as determined by the width of the adhesive collar.

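### Hypothesis 1.1 concerns post-treatment and 3 months, but no contrast at either visit is pre-specified; both are left to post-hoc tests of a significant treatment-by-time interaction, without baseline adjustment

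*Combined protocol and SAP*

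**What the plan says.** In Data Analyses, Primary Aim 1 Hypothesis 1.1, MBSR participants are predicted to report lower "self-reported anger and aggression at post-treatment and at the 3-month follow up compared to those assigned to the TREC group". STAXI-2 and BPAQ are analysed separately with "mixed effects models with treatment, time, and treatment x time interaction as fixed effects", with subject nested in a random therapy group. On visit-level comparisons the section says only "Significant interactions will be examined further using post-hoc tests". On multiplicity it says "Bonferroni adjustments will be implemented to control for Type 1 error", without giving an alpha or the number of tests it is divided over.

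Table 1 has both outcomes measured at five visits: baseline, week 3, week 6, post-treatment and 3 months ("State Trait Anger Expression Inventory-2 (STAXI-2) | X | X | X | X | X"; BPAQ has the same row). The model is justified partly because such models can be fitted so that "they use all available data on an individual". The section does not say whether time is categorical or continuous, or which visits enter the test.

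The Data Analyses preamble adds covariates on which the arms are found to differ, from an open list, plus medication use (yes/no). It does not name the baseline STAXI-2 or BPAQ score.

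Sample Size and Power Considerations describes the trial as a pilot that may be too small for significance. It plans a two-sample t-test of the baseline-to-post-treatment change to obtain effect sizes, with confidence intervals, for a later trial.

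**The concern.** The hypothesis is about two visits, while the only test described is about the whole profile over time. A treatment-by-time interaction asks whether the arm difference is the same at every visit, baseline included. It does not ask whether the arms differ at post-treatment or at 3 months. The answers can disagree in both directions: a transient difference during treatment can make the interaction significant, and a real difference at a hypothesised visit can go with a non-significant interaction. In the second case the plan does not say what will be reported.

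Baseline is the other part. With baseline as one level of time and a free mean in each arm, any visit contrast from the interaction is a difference in change from baseline. That is valid but less precise than adjusting for the baseline score. It also leaves regression-to-the-mean error from chance baseline imbalance, which matters with about 60/6 = 10 randomised groups. At stake are a primary test that answers the stated question and the precision of the estimates on which the later trial is to be planned.

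**Working it through.** **Inputs.** From the documents: 60 veterans; two hypothesised visits; five measurement visits; two self-report outcomes; allocation in groups of six. The documents give no arm size, alpha, SD, effect size or correlation between visits, so there is no stated figure to reproduce. Assumed throughout: 30 per arm, SD 1, equal correlation r between visits, no dropout and no clustering. An overall two-sided 0.05 gives 0.05/2 = 0.025 per outcome, or 0.05/4 = 0.0125 per outcome and visit. Time is taken as a five-level factor, so the interaction has 4 and 232 degrees of freedom.

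**1. Can the interaction be significant with no difference at the hypothesised visits?** The noncentrality is λ = (n/2) Σ(δj − δ̄)² / (1 − r), where δj is the arm difference at visit j. Put 0.65 SD at weeks 3 and 6 and zero elsewhere. Then δ̄ = 0.26, and the sum is 2(0.39²) + 3(0.26²) = 0.507.
- r = 0.5: λ = 15 × 0.507/0.5 = 15.2, power 0.83 at alpha 0.025.
- r = 0.7: λ = 15 × 0.507/0.3 = 25.4, power 0.98.

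Simulation (20,000 trials per setting) agrees: 83% and 98%.

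**2. Can it be non-significant when a hypothesised visit differs?** Simulated power for the post-treatment change contrast at 0.025, effect 0.65 SD at the last two visits:

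| Shape over the four post-baseline visits | r | Not gated | Only after a significant interaction |
|---|---|---|---|
| Gradual (3/8, 6/8, 1, 1) | 0.5 | 0.61 | 0.48 |
| Gradual | 0.7 | 0.84 | 0.77 |
| Late (0, 0, 1, 1) | 0.5 | 0.61 | 0.57 |
| Late | 0.7 | 0.84 | 0.84 |

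In the first row, 21% of trials had a contrast significant at 0.025 at post-treatment or 3 months together with a non-significant interaction.

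**3. Precision.** Per-person variance is 2(1 − r) for a change score and 1 − r² after adjustment for baseline. The ratio is 2(1 − r)/(1 − r²) = 2/(1 + r): 1.54 at r = 0.3, 1.33 at r = 0.5, 1.18 at r = 0.7.

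**4. Does the interaction test lose power overall?** Take d = 0.5 and r = 0.6. The adjusted post-treatment contrast has noncentrality 0.5/√(2 × 0.64/30) = 2.42. The ranges below reflect 57 to 232 residual degrees of freedom.

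| Shape (share of d at the five visits) | Interaction, 0.025 | Adjusted post contrast, 0.025 | Adjusted post contrast, 0.0125 |
|---|---|---|---|
| Gradual (0, 0.25, 0.6, 1, 1) | 45% | 55–57% | 44–46% |
| Fading (0, 0.3, 0.7, 1, 0.5) | 31% | 55–57% | 44–46% |
| Late (0, 0, 0, 1, 1) | 67% | 55–57% | 44–46% |

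The interaction test is weaker for gradual and fading effects at 0.025 and stronger for a late one. For the gradual effect, splitting alpha over both visits brings the adjusted contrast back to about the level of the interaction test.

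**The case against.** A reader might infer that the plan wastes power. The documents do not support that as a general statement. They give no effect size or correlation, and step 4 shows that the answer turns on the shape of the effect and the alpha split. In the gradual case, an unadjusted change contrast at 0.025 has 45–46% power against 45% for the interaction. There the advantage of the adjusted contrast comes almost wholly from the baseline adjustment.

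A reader might also infer that a five-visit, 4-df test is prescribed, or that visit estimates will be withheld unless the interaction is significant. Neither is stated. Both are natural readings of Table 1 and of the post-hoc sentence, but the plan is silent. The silence is itself a gap: a linear time effect would be a 1-df test that fits a two-visit hypothesis no better.

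Nor is baseline ignored. The interaction nets it out, and the open covariate rule could admit the baseline score if the arms were found to differ. What remains is that adjustment is not pre-specified and, under that rule, would depend on the observed imbalance.

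The strongest defence is that this is a declared pilot, and Sample Size and Power Considerations already gives a baseline-to-post effect size with a confidence interval that does not depend on the interaction. That stands for post-treatment. It supplies no 3-month contrast, no baseline adjustment and no therapy-group term. A pilot meant to inform a later trial also has the least use for estimates that appear only after a significant test.

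**Conclusion.** The concern holds as a mismatch between hypothesis and test, plus an avoidable loss of precision. No contrast at post-treatment or 3 months is pre-specified, and the only route to one is post-hoc. On the five-visit reading, a pattern confined to weeks 3 and 6 would be significant in 83% to 98% of trials at 0.65 SD, while a gradual effect of that size at r = 0.5 would see post-treatment power fall from 0.61 to 0.48 through the gate. Change-score contrasts have 1.18 to 1.33 times the variance of adjusted ones for r between 0.7 and 0.5.

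These sizes rest on the assumed 30 per arm, equal correlations, complete data and alpha 0.025 per outcome. Therapy-group clustering and dropout were not modelled; they would generally lower the powers, and the gain under the nested model is not known. The mismatch itself depends on none of these figures. It should be corrected, but it is not evidence that the planned model is invalid or generally underpowered relative to the alternative.

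**What to change.** Keep the mixed model and its therapy-group random effect, and amend the Hypothesis 1.1 text as follows:

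- State that time is categorical and which visits enter.
- Constrain the two arms to a common baseline mean, or use the baseline score as a covariate with the four post-baseline visits as outcomes. Baseline is measured before allocation, so either is legitimate.
- For each of STAXI-2 and BPAQ, name the adjusted MBSR–TREC difference at post-treatment as the primary contrast and at 3 months as the second.
- State the overall alpha and how Bonferroni divides it across outcomes and visits.
- Report both contrasts with confidence intervals whether or not the interaction is significant, and treat the interaction as descriptive.

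The cost is wording only; no new data are needed. One trade-off should be decided openly: dividing alpha over both visits as well as both outcomes (0.0125 each) uses up most of any power gain. The firm benefits are a test that matches the hypothesis and more precise, unconditional estimates for planning the later trial.
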